10.2. Reporting Related Serious Adverse Events to ICR-CTSU

Safety reporting requirements for OTIS-S are limited to only related (to study procedure) SAEs as defined in Section 10.1. Study procedures are limited to the imaging interventions and the blood draws for the miRNA testing. Any related SAE that occurs from the time of baseline imaging and up to 30 days following the last blood draw must be reported.

The severity of AEs should be graded according to the NCI-CTCAE criteria version 5.

Whenever one or more sign/symptom corresponds to a disease or a well-defined syndrome only the main disease/syndrome should be reported.

All related SAEs should be reported to ICR-CTSU within 24 hours of the Principal Investigator (or designated representative) becoming aware of the event, by completing the OTIS-S SAE form in the trial database. As much information as possible, including the Principal Investigator's assessment of causality, must be reported to ICR-CTSU in the first instance. Additional follow-up information should be reported as soon as it is available.

All SAE forms must be completed, signed and dated by the Principal Investigator or designated representative.

Data on serious adverse events that do not meet the above definition of a related SAE will not be collected.

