2.2. Secondary Objectives**Part A:**

- To demonstrate high specificity of miRNA for relapse detection in this setting
- To demonstrate feasibility and acceptability to patients of miRNA monitoring in this setting
- To quantify the lead time (extent to which relapse diagnosis can be bought forward) associated with miRNA monitoring when compared with standard surveillance

Part B:

- To demonstrate cost-effectiveness of miRNA monitoring compared with standard surveillance
- To demonstrate reduced use of imaging and subsequent impact on radiation exposure with miRNA monitoring compared with standard imaging-based surveillance
- To further evaluate acceptability to patients of miRNA monitoring in this setting
- To quantify anxiety, fear of recurrence and health-related quality of life for patients managed with the two different approaches to surveillance
- To understand any impact on disease outcomes and subsequent treatment associated with use of miRNA monitoring in place of standard imaging
- To understand the risk-benefit balance of a miRNA monitoring approach (when compared to standard surveillance) from the perspective of different stakeholders, including patients

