In the event that miRNA remains positive, but relapse has not been confirmed on imaging as part of the above process, this should also be discussed with the trial team to determine appropriate management on a case-by-case basis. Where no more surveillance imaging is scheduled (i.e. >36 months post-randomisation),

it may be appropriate to schedule a further imaging investigation 6 months after previous scan (i.e. approximately 9m after the first positive miRNA result).

Please note that the investigations detailed above are the minimum requirements for trial purposes; other investigations can be carried out on a case-by-case basis as deemed appropriate by the local investigator.

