9.3. Supportive care

All medication considered necessary for the participants' welfare and which is not expected to interfere with the evaluation of the intervention may be given at the discretion of the investigator. All medications (including start/stop dates, dose frequency, route of administration and indication), must be recorded in the participant's clinic notes, as well as the appropriate pages of the eCRF.

10. Safety Reporting

As the study intervention in OTIS-S is limited to blood draws, imaging scans and questionnaire completion, reporting requirements for OTIS-S are limited to direct study-related procedure SAEs as defined in Section 10.1.

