10.1. Definitions

Adverse Event (AE)

An AE is any untoward medical occurrence in a trial participant receiving a study intervention; the event does not necessarily have a causal relationship with the procedure. Study interventions for OTIS-S are limited to blood draws and scans, i.e. CT, MRI or ultrasound scans. Adverse events not meeting the criteria of serious will not be collected.

Serious Adverse Event (SAE)

An SAE is any untoward medical occurrence that occurs from baseline and within 30 days of the last study intervention (in OTIS-S this will be the blood draws and imaging assessments performed during follow-up) and:

- results in death

- is life-threatening
- requires hospitalisation or prolongation of existing inpatients' hospitalisation
- results in persistent or significant disability or incapacity
- is a congenital anomaly or birth defect

Important adverse events that are not immediately life-threatening or do not result in death or hospitalisation but may jeopardise the subject or may require intervention to prevent one of the other outcomes listed in the definition above, may also be considered serious.

Progression of the indicated disease and death due to progression of the indicated disease are not considered SAEs.

Definitions of causality

| Relationship | Description |
|----------------|--|
| Unrelated | There is no evidence of any causal relationship with the trial procedure. |
| Unlikely | There is little evidence to suggest there is a causal relationship (e.g. the event did not occur within a reasonable time after administration of the trial procedure). There is another reasonable explanation for the event (e.g. the patient's clinical condition, other concomitant treatment). |
| Possible | There is some evidence to suggest a causal relationship (e.g. because the event occurs within a reasonable time after administration of the trial procedure). However, the influence of other factors may have contributed to the event (e.g. the patient's clinical condition, other concomitant treatments). |
| Probable | There is evidence to suggest a causal relationship, and the influence of other factors is unlikely. |
| Definitely | There is clear evidence to suggest a causal relationship, and other possible contributing factors can be ruled out. |
| Not assessable | There is insufficient or incomplete evidence to make a clinical judgement of the causal relationship. |

Related Unexpected Serious Adverse Event (RU-SAE)

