An adverse event that meets the definition of serious and is assessed by the CI or nominative representative as:

- “Related” – that is, it resulted from administration of any of the research procedures, and
- “Unexpected” - for the purposes of OTIS-S all serious and related adverse events will be considered unexpected

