11.4. Interim Analyses and Stopping Rules

An Independent Data Monitoring Committee (IDMC) will be formed and will confidentially review accumulating data on primary and secondary endpoints.

Prior to the primary analysis for Part A, relapses within the trial will be monitored on an ongoing basis by the IDMC. If, before 11 relapses detected on routine imaging have occurred, >1 relapse is not correctly identified on miRNA, and noting that participant safety is not compromised (all Part A participants have routine imaging), the oversight committees will consider the value of continued recruitment to support planned analyses of all Part A endpoints.

For each of the planned analyses in Part A (described in 11.2), the IDMC will review results and make recommendations to the Trial Steering Committee (TSC) regarding continuation of the trial, considering the pre-specified progression criteria outlined in 11.3.1.

During Part B, the IDMC will continue to monitor accumulating data at regular intervals (at least annually). Given the non-inferiority hypothesis, and that primary endpoint events will accrue slowly relative to recruitment timescales, early stopping on the basis of efficacy is not expected to be relevant and so no formal interim analysis or stopping rules are in place. However, at each review, the IDMC will consider the balance of risks and benefits in the accumulating data, as well as any emerging external evidence, in making recommendations to the TSC regarding continuation of the trial.

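### Related-SAE reporting stops at blood draws and scans, so serious complications of investigation or treatment prompted by a surveillance result are not collected and are no named endpoint

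*Protocol*

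**What the plan says.** The opening of Protocol section 10 states that "reporting requirements for OTIS-S are limited to direct study-related procedure SAEs as defined in Section 10.1". Section 10.1 then says "Study interventions for OTIS-S are limited to blood draws and scans, i.e. CT, MRI or ultrasound scans", and defines a related event by the condition "that is, it resulted from administration of any of the research procedures". Section 10.2 repeats the limit, "Study procedures are limited to the imaging interventions and the blood draws for the miRNA testing", and closes the door on the rest: "Data on serious adverse events that do not meet the above definition of a related SAE will not be collected".

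Section 7.4.2 sets the work-up after a positive miRNA result: MRI or CT, then FDG PET-CT if that is negative, then markers, further miRNA samples and repeat imaging. Persistent positives without confirmed relapse go to the trial team for case-by-case management. The listed steps are a minimum, and "other investigations can be carried out on a case-by-case basis as deemed appropriate by the local investigator".

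Section 2.2 includes the Part B objective "To understand the risk-benefit balance of a miRNA monitoring approach" compared with standard surveillance, from the perspective of different stakeholders. For Part B, section 11.4 says that at each review "the IDMC will consider the balance of risks and benefits in the accumulating data".

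**The concern.** The miRNA result is fed back in real time and acted on, and in Part B it replaces routine imaging. Part of the risk of a surveillance test lies in what is done because of its result, beyond the needle or the scanner. If a participant with a positive result and negative scans has an invasive investigation or is treated, and a serious complication follows, that event did not result from a blood draw or a scan. Under 10.2 it is not a related SAE, so it is not collected.

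At stake is one component of the risk side of the Part B objective and of the IDMC's reviews. If such events occur, those weighing risk and benefit would have no systematic count of them.

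**Working it through.** **Step 1. Does the text exclude these events?** Yes. Section 10.1 ties a related event to the administration of a research procedure, 10.2 lists those procedures as imaging and miRNA blood draws, and SAEs outside that definition are not collected. A complication of a biopsy or operation, or of treatment given because of the result, meets none of these conditions. Biopsy and operation are illustrations here; section 7.4.2 names neither. Serious harm from a triggered scan is covered, since 10.2 includes imaging.

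**Step 2. Does another planned item record them?**
- Specificity (11.2.2) counts positive results in non-relapsing participants, not what followed. It is a Part A endpoint, analysed at the final analysis (11.3.1).
- Central review (9.2) collects the scans of unconfirmed positives, not procedures or complications.
- Section 7.6 collects relapse details and treatment after recurrence is confirmed on imaging.
- Section 9.3 requires medications to be recorded on the eCRF, with indication. It does not cover procedures or their complications.
- Part B endpoints (3.2, 11.2.4) cover imaging numbers, radiation, adherence, acceptability, anxiety and fear of recurrence, HRQoL, DFS, treatment for relapse, OS, second malignancies and cost-effectiveness. Advanced relapse is the primary endpoint.
- Routine NHS data (3.2) may show hospital care, but they are named for cost-effectiveness and carry no stated link to a surveillance result.

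None of these names a serious complication of a prompted investigation or treatment.

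**Step 3. How many participants could be exposed?** The plan states no figure, so this is for scale only.

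Inputs: 1 of 23 patients without recurrence had raised miRNA in the pilot (1.1.3); 0 of 60 controls were positive under the refined thresholds (1.1.3); 12% relapse and about 260 participants in Part A (11.1.1); 345 seminoma participants in the Part B miRNA arm, plus 20 of the 40 dysgerminoma participants at 1:1 (11.1.2).

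Non-relapsers, taking 12% relapse for all:
- Part A: 260 × 0.88 = 228.8
- Part B miRNA arm: (345 + 20) × 0.88 = 321.2

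Pilot rate: 1/23 = 4.3%, exact 95% CI 0.11% to 21.9%.
- Part A: 228.8 / 23 = 9.9; limits 228.8 × 0.0011 = 0.3 and 228.8 × 0.2195 = 50
- Part B miRNA arm: 321.2 / 23 = 14.0; limits 0.4 and 70

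Controls: 0/60, with exact upper 95% limit 1 − 0.025^(1/60) = 6.0%. I read this as one sample per control. Participants have 10 real-time samples each (9.1.1), so a per-sample rate p accumulates to 1 − (1 − p)^10 if tests are independent. Assuming p from 0.1% to 1%, the share with at least one false positive is 1.0% to 9.6%, or 2 to 22 of the 228.8 in Part A.

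These are counts of positive results, not of harms. The documents give no rate of invasive work-up or of its complications, so the chain stops here.

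**Step 4. Are the definitions consistent among themselves?** Not fully. Section 7.4.2 requires FDG PET-CT after a positive result with negative imaging. The scan list in 10.1 names CT, MRI and ultrasound only, while 10.2 speaks of imaging in general. Whether PET-CT counts as a study procedure depends on which section is read.

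**The case against.** Limiting SAE reporting to trial procedures is a deliberate choice, stated consistently across section 10 apart from the PET-CT point. The mandated work-up is non-invasive, and relapse treatment follows confirmation on imaging (7.6). An invasive step can enter only through the discretionary clause or case-by-case management. Persistent unconfirmed positives must be discussed with the trial team, so they are visible centrally. Part B details are deferred to an amendment. All of this stands and keeps the gap small. It does not close it: discussion with the trial team is not data collection, and section 10 is neither marked as Part A only nor listed for revision.

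A reader might go further and infer three things that the documents do not support.

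- That the excluded events are the main harm of the test. The protocol treats late or missed detection as the principal risk of replacing imaging and makes advanced relapse the Part B primary endpoint.
- That the comparison is tilted toward miRNA. Section 10 is not arm-specific, so a complication after a false-positive or equivocal scan in the control arm goes uncollected as well. No rate is given for either arm, so the direction is unknown.
- That the decision to start Part B rests on incomplete safety data. The rule in 11.3.1 requires at least 10 of 11 relapses detected and no concerns on secondary endpoints; SAE data are not a stated criterion.

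**Conclusion.** The concern holds in a narrow form. By stated rule, serious complications of investigation or treatment prompted by a trial surveillance result are not collected as SAEs, and no endpoint names them. The section 2.2 objective and the IDMC's risk-benefit review therefore lack that component, while the other main risks and burdens are measured.

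About 10 Part A participants might have a positive result without relapse, with a range of 0.3 to 50 that mostly reflects a pilot of 23 patients; the control data point lower. This rests on the pilot rate carrying over to this trial and on 12% relapse. The number of missed SAEs cannot be calculated and may be very small or zero. This is a cheap improvement and not a threat to the trial's validity.

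**What to change.** - In 10.1 and 10.2, extend the definition of related to any SAE resulting from an investigation or treatment undertaken because of a trial surveillance result. Apply it to both arms in Part B, so that events prompted by scans and by miRNA are counted alike. Word the reporting window, which 10.2 ends 30 days after the last blood draw, so that it covers the prompted procedure.
- For each participant with a positive miRNA result not confirmed on imaging, record on the eCRF any invasive investigation or treatment it prompted. Show these counts to the IDMC beside specificity.
- In the same edit, reconcile the scan list in 10.1 with the FDG PET-CT required in 7.4.2.

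The change is best made now, so that Part A cases are captured, and carried into the planned Part B amendment. The cost is a change of wording, one short eCRF page and a few more SAE forms. The downside is that sites must judge whether a procedure was prompted by the surveillance result. Only reporting changes; clinical management stays as it is.

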10.3. Review of Related Serious Adverse Events

The Chief Investigator (or designated representative) will assess all reported related SAEs for causality (NB. The Chief Investigator cannot down-grade the Principal Investigator's assessment of causality) and, for OTIS-S, all serious and related AEs will be considered unexpected.

RU-SAEs will undergo expedited reporting to the relevant authorities and all other interested parties by ICR-CTSU.

Sites should respond as soon as possible to requests from the Chief Investigator or designated representative (via ICR-CTSU) for further information that may be required for final assessment of a related SAE.

10.4. Expedited Reporting of Related Unexpected SAEs

All RU-SAEs will be reported by ICR-CTSU to the main REC, the Sponsor and all other interested parties within 15 days of being notified of the event.

The Principal Investigators at all actively recruiting sites will be informed of RU-SAEs occurring within the trial at appropriate intervals.

10.5. Follow up of Serious Adverse Events

The PI should actively seek follow up information on reported SAEs. All related SAEs should be followed up until clinical recovery is complete or until disease has stabilised. Related SAE outcomes should be reported to ICR-CTSU using the relevant section of the SAE form as soon as the Principal Investigator or designee becomes aware of the outcome.

10.6. Reporting Pregnancies

If any trial participant becomes pregnant while taking part in the OTIS-S trial, this should be reported to ICR-CTSU using the pregnancy reporting form. Participants who become pregnant should be discussed with the Chief Investigator or delegate and may continue in the trial but with adaptations to the imaging protocol as appropriate. The participant should not be exposed to ionising radiation until the pregnancy is completed. Pregnancies should be followed up until conclusion and all follow-up information should be reported to ICR-CTSU. If the outcome of the pregnancy meets the definition of serious (i.e. congenital abnormality)

this should be reported to ICR-CTSU following the serious adverse event reporting procedures described above.

11. STATISTICAL CONSIDERATIONS

11.1. Statistical Design, Intervention Allocation and Sample Size Justification

11.1.1. Part A Statistical Design

Part A will use a phase II, A'Hern single arm design³⁷ with all participants receiving the intervention (miRNA monitoring) alongside standard surveillance imaging.

The aim is to demonstrate that miRNA sensitivity exceeds a pre-specified threshold and, hence, sample size is driven by the number of relapses. The sample size is based on the combined cohort (seminoma and dysgerminoma), since differences are not anticipated, and this will allow more timely progression to Part B.

Sensitivity of miRNA for relapse detection is expected to be at least 95% based on previous studies³⁰. Sensitivity >75% is deemed appropriate to warrant further study (i.e. progression to Part B) and, ultimately, the aim is to demonstrate that sensitivity exceeds 85%. For this phase II evaluation, a one-sided alpha of 0.2 will be used. The higher “false positive” risk associated with using a higher alpha than might traditionally be used will facilitate a timely decision regarding initiation of the Part B which will provide a confirmatory evaluation. Subsequent analyses of the Part A cohort, when more relapses have been observed, will achieve greater precision in estimating sensitivity.

In order to have 80% power to show sensitivity >75%, with one-sided alpha of 0.2, a total of 11 relapses need to be observed. If at least 10 of these are correctly identified on miRNA at the same time or before being identified on imaging, a sensitivity $\leq 75\%$ could be excluded. Two further analyses will be performed when 21 and 28 relapses have occurred with the aim of showing sensitivity >80% and >85% respectively, requiring at least 19 of 21 and at least 26 of 28 relapses to be detected on miRNA. Power for both of these analyses (using one-sided alpha of 0.2) will be >80%. Calculations were performed using Stata version 17.0.

In order to determine required sample size, projected numbers of relapses have been based on TRISST relapse patterns and recruitment rates; 12% of participants are expected to relapse, nearly all within 36 months¹⁶. Although relapse rates may be slightly higher for dysgerminoma, these patients are expected to only make up a very small proportion of the cohort³⁸. In order to achieve a relatively seamless transition to Part B, recruitment to part A will continue up until 11 relapses are observed at which point the primary analysis, aimed at demonstrating sensitivity >75%, will be performed. The expected sample size to be recruited during this period is **approximately 260 participants**. Further follow-up of this cohort will allow the later, updated analyses to be performed, increasing the precision with which sensitivity can be estimated.

11.1.2. Part B Statistical Design

Part B will use a phase III, randomised design to test the non-inferiority hypothesis that there is no unacceptable increase in risk of advanced relapse ($\geq 3\text{cm}$ or CSIII) when miRNA monitoring is used in place of standard surveillance imaging.

Seminoma participants will be allocated 2:1 to miRNA monitoring (intervention) or standard surveillance imaging (control) using computer-generated random permuted blocks.

Randomisation will be stratified by surveillance imaging type (MRI/CT), age group (≤ 29 , $30-39$, ≥ 40 years) and prognostic group (low, intermediate or high, based on European Association for Urology risk classification³⁹). Dysgerminoma participants will be allocated 1:1 between miRNA monitoring or standard surveillance imaging (control) with randomisation stratified by age group only (≤ 18 years or ≥ 19 years).

As for Part A, the primary analysis will consider the combined seminoma and dysgerminoma cohort but, for this confirmatory component, a separate analysis of the seminoma cohort will also be adequately powered. For the dysgerminoma cohort, where there is more uncertainty around event rate and it would not be feasible to achieve a fully powered cohort, evidence pertaining to this group will be based on consistency of outcomes (primary and secondary) between the two cohorts.

Based on the TRISST trial, 4.5% of seminoma patients are expected to relapse with advanced disease on a 3-scan imaging schedule¹⁶. Part B will be designed to have 80% power to exclude a doubling of this rate (non-inferiority margin 4.5%) with a one-sided 5% alpha. Allowing for a 15% dropout rate (again, based on TRISST), this requires 345 seminoma participants per arm based on a 1:1 randomisation. This was calculated in Stata version 17.0 using the ART (Analysis of Resources for Trials) package, binary version 2.1.0.

A 1:1 randomisation would lead to a prohibitively large sample size; however, the TRISST trial provides robust data on outcomes in a large, contemporary cohort undergoing standard surveillance, in a population expected to be very similar to the seminoma participants recruited to OTIS-S. This data will be used to supplement control data from within OTIS-S, allowing for a smaller within-trial control arm^{33,40}. As such, **518 seminoma participants** will be allocated 2:1 to miRNA ($n=345$) or standard surveillance ($n=173$). Since previous datasets on outcomes for dysgerminoma patients are less robust, allocation will be 1:1 for this group. **40 dysgerminoma participants** are expected to be recruited in the timeframe required for seminoma recruitment. Thus, the **total target sample size for part B is 558**.

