3. TRIAL DESIGN

This is a multicentre, seamless phase II/III trial which will recruit a total of 818 participants with stage I seminoma or dysgerminoma. The intervention is the collection of blood samples for the purpose of miRNA monitoring. The staged approach to evaluation will allow experience and confidence with miRNA monitoring to build over time in both patient and clinical communities and facilitate implementation into routine practice, if warranted by the results.

Part A (phase II) will use a single-arm approach in which approximately 260 participants will undergo miRNA monitoring alongside standard surveillance with the aim of demonstrating that miRNA exceeds a pre-specified level of sensitivity for relapse detection.

If warranted by results from part A, 558 participants will be enrolled in part B (phase III) and will be randomly allocated 2:1 to miRNA monitoring with triggered imaging only (no routine imaging) OR standard surveillance imaging. Control arm data will be augmented by data from a previous trial in this setting, utilising Bayesian methods, as an efficient approach which allows for a smaller within-trial control group³²⁻³⁴.

Inclusion of two biologically-similar tumour types (seminoma and dysgerminoma) within a single protocol will allow evidence to be gained for a rare tumour type (dysgerminoma, where a separate, fully-powered trial would not be feasible), through assessing consistency with the seminoma cohort in terms of primary and secondary endpoints³².

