11.2.3. Part B Primary Endpoint

The primary endpoint for Part B is the number of advanced relapses, defined as those with mass size (maximum short axis diameter) $\geq 3\text{cm}$ and/or clinical stage III. The time point of interest is 3 years and Kaplan-Meier estimation will be used, with censoring at the last disease assessment for those participants lost to follow-up before 3 years.

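### Part B pools seminoma (randomised 2:1) with dysgerminoma (randomised 1:1); the combined primary estimate should be formed within tumour type, and section 3 reconciled with these ratios

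*Protocol*

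**What the plan says.** Protocol section 11.1.2 sets up two allocation schemes. Seminoma is allocated 2:1 in favour of miRNA, giving 345 and 173 of 518 participants. For the other tumour type, "Dysgerminoma participants will be allocated 1:1 between miRNA monitoring or standard surveillance imaging (control) with randomisation stratified by age group only"; 40 such participants are expected. The section then states that "the primary analysis will consider the combined seminoma and dysgerminoma cohort" and adds a separate seminoma analysis, described as adequately powered. TRISST data will supplement the seminoma controls, but the weight is not given.

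On estimation, section 11.2.3 says "The time point of interest is 3 years and Kaplan-Meier estimation will be used". Neither section mentions stratification by, or adjustment for, tumour type in the combined analysis.

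On event rates, section 11.1.2 expects 4.5% advanced relapse in seminoma. It gives no figure for dysgerminoma and calls that rate more uncertain. Section 11.1.1, planning Part A and speaking of relapse overall, begins a sentence "Although relapse rates may be slightly higher for dysgerminoma".

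Section 3 describes the 558 Part B participants as a single group who "will be randomly allocated 2:1 to miRNA monitoring with triggered imaging only" or standard imaging. Section 11.3 leaves the detail of the Part B analyses to a later amendment and a Part B SAP.

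**The concern.** When two strata are randomised in different ratios and then pooled, stratum and arm are associated by design. If the strata have different event rates, the crude arms differ even when the intervention does nothing. Here dysgerminoma takes up a larger share of the randomised control arm than of the miRNA arm. If its advanced-relapse rate is the higher one, the crude control rate is raised and miRNA monitoring looks better than it is. In a non-inferiority trial that is the anti-conservative direction.

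Section 11.1.2 introduces the pooling by analogy with Part A. Part A has a single arm, so pooling there cannot mix tumour type with arm. In Part B it can.

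Adding external controls that are all seminoma shifts the control-arm mix again, by an amount that depends on how much is borrowed. The size and sign of any bias in a crude analysis would then follow from the borrowing weight.

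**Working it through.** **Inputs.** From section 11.1.2: seminoma 345 miRNA and 173 control; dysgerminoma 40 at 1:1, so 20 and 20; seminoma advanced-relapse rate 4.5%; margin 4.5 points; one-sided alpha 5%; power 80%; dropout 15%. The dysgerminoma advanced-relapse rate is an assumption, varied from 2% to 20%. The effective number of borrowed controls, B, is also an assumption.

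**The plan's own figure.** Take 4.5% in both arms with a 4.5-point margin. Use the null variance at the constrained maximum-likelihood estimate (Farrington-Manning) and the unpooled alternative variance. The constrained rates are 3.14% and 7.64%, so the variances are 0.1010 (null) and 0.0860 (alternative). Then n = (1.645 × √0.1010 + 0.842 × √0.0860)² / 0.045² = 292.5, rounded up to 293 per arm; 293/0.85 = 344.7, so 345. The total is 345 + 173 + 40 = 558. Both figures reproduce.

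**Mix by arm.** miRNA: 20/(345 + 20) = 5.5%. Within-trial control: 20/(173 + 20) = 10.4%. The gap is 4.9 points. The overall ratio is 365:193, about 1.9:1.

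**Bias of a crude pooled difference, within-trial data only.** With no true effect, the crude rates are (345 × 4.5% + 20 × pD)/365 and (173 × 4.5% + 20 × pD)/193, so

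bias = (20/365 − 20/193) × (pD − 4.5%) = −0.0488 × (pD − 4.5%).

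Type I error is by normal approximation with 85% evaluable and a true difference equal to the margin in both tumour types. At pD = 9% the crude rates are then 9.25% and 4.97%, the difference is 4.28 points and its standard error is 2.36 points. The error is Φ((4.50 − 4.28)/2.36 − 1.645) = 6.0%.

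| Assumed pD | miRNA | Control | Bias (points) | Share of margin | Type I error |
|---|---|---|---|---|---|
| 2% | 4.36% | 4.24% | +0.12 | 2.7% | 4.5% |
| 6% | 4.58% | 4.66% | −0.07 | 1.6% | 5.3% |
| 9% | 4.75% | 4.97% | −0.22 | 4.9% | 6.0% |
| 12% | 4.91% | 5.28% | −0.37 | 8.1% | 6.8% |
| 20% | 5.35% | 6.11% | −0.76 | 16.8% | 8.9% |

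A negative sign favours non-inferiority.

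**With borrowed seminoma controls.** The control share becomes 20/(193 + B). It equals 20/365 when B = 365 − 193 = 172, and the bias is then exactly zero at any pD. With B = 345 the share is 20/538 = 3.7% and the sign reverses: at pD = 9% the bias is (5.48% − 3.72%) × 4.5 = +0.08 points and type I error is 4.6%; at 20% type I error is 3.7%.

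**Contrast formed within tumour type.** With Mantel-Haenszel weights the bias is zero and type I error is 5.0% at every pD and B tried. Power at true equality:

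| Controls | pD | Stratified | Crude |
|---|---|---|---|
| Borrowed to an effective 345 | 4.5% | 85.5% | 85.5% |
| Borrowed to an effective 345 | 9% | 84.0% | 83.9% |
| Within-trial only | 4.5% | 72.4% | 72.7% |
| Within-trial only | 9% | 69.8% | 73.3% |

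In the last row the crude figure is helped by its own bias. The borrowing rows treat borrowed controls as exchangeable with the trial's own.

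**The case against.** The strongest reply is that the protocol nowhere prescribes a crude pooled analysis. Section 11.3 defers Part B analysis detail to an amendment and SAP, and stratification commonly belongs there. Naming a population and a Kaplan-Meier time point does not exclude it. Randomisation is run separately for each tumour type, so a valid randomised contrast is available within each. This stands. A reader might infer that the Part B comparison is biased as designed, or that randomisation does not protect it. The documents do not support that: bias arises only if the analysis ignores tumour type.

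The second reply is that the within-trial figures describe an analysis that is not planned, since sections 3 and 11.1.2 commit to augmenting the control arm. The design figures (345 per arm at 1:1, 173 recruited) point towards an effective 172 borrowed controls, where the bias vanishes. This also stands, but the weight is not stated, so zero cannot be assumed.

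Third, a reader might take the larger figures as the likely size. Advanced-relapse rates of 15% or 20% would exceed the 12% that section 11.1.1 expects for all relapse. The document speaks only of a modest increase, and of relapse overall. Even 9% is a doubling of the seminoma rate.

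Fourth, the powered seminoma analysis covers 518 of 558 participants (93%) and is free of the problem, so a misleading combined result would sit beside an unaffected one. That is a real safeguard, but it is not the primary analysis.

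What remains is more than missing detail. The protocol already fixes unequal allocation, a pooled primary population and the estimator, and together these call for one qualifying sentence.

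**Conclusion.** The point holds as a free improvement of minor to moderate importance. A crude combined comparison would be confounded by tumour type: 5.5% against 10.4% dysgerminoma by arm in the within-trial data. At assumed dysgerminoma rates of 6% to 9%, the bias is 0.07 to 0.22 points towards non-inferiority, or 1.6% to 4.9% of the margin, with type I error of about 5.3% to 6.0%. It grows beyond that only at rates well above a modest excess. Under borrowing it can vanish or reverse, so neither its size nor its direction can be stated until the weight is known. If dysgerminoma had the lower rate, the within-trial direction would also reverse. The dysgerminoma rates and borrowing amounts are assumptions; the arm shares follow from the protocol's numbers.

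The conflict between section 3 (2:1 for all 558) and section 11.1.2 (2:1 for seminoma, 1:1 for dysgerminoma) needs no assumption. It is a wording inconsistency and does not itself show bias.

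**What to change.** In the Part B amendment, and in sections 11.1.2 and 11.2.3:

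- State that the combined primary estimate is formed within tumour type: 3-year Kaplan-Meier risk differences in seminoma and in dysgerminoma, combined with weights set in advance, for example Mantel-Haenszel. Weights based on numbers of participants are safer than inverse-variance weights, because 20 dysgerminoma participants per arm would yield only about 20 × 4.5% = 0.9 to 20 × 9% = 1.8 events.
- Confine the TRISST borrowing to the seminoma stratum.
- Reconcile section 3 with the allocation ratios in section 11.1.2.

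The cost is wording. The sample size does not change. With borrowing to an effective 345 seminoma controls, power is practically the same as for the crude analysis. Without borrowing, the stratified analysis has 0.3 points less power at a 4.5% dysgerminoma rate and 3.5 points less at 9%, where the crude analysis does not hold its 5% error.
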